4.4 Notification of deaths

Due to the nature of the condition of interest, a high proportion of deaths is expected. Reports of deaths will be made to the SMG every month and reviewed by the SOC every 6 months.

4.5 Reporting urgent safety measures

If any urgent safety measures are taken the CI/Sponsor shall immediately and in any event no later than 3 days from the date the measures are taken, give written notice to the relevant REC of the measures taken and the circumstances giving rise to those measures.

5. DATA MANAGEMENT

A Data Management Plan will be created in accordance with University of Warwick SOPs.

Personal data collected during the study will be handled and stored in accordance with the Data Protection Act 2018 which encompassed the requirements of the EU General Data Protection Regulations and Warwick CTU SOP 15 'Data Management'.

For this feasibility study, participants will be identified using a unique study number only. Personal identifiable data will be shared between the Ambulance service and the receiving hospital for the purpose of follow-up to hospital discharge. Outcome data for those patients missed in hospital will be sought by the Ambulance Service from the patient's GP. Personal identifiable information will therefore be shared between these agencies for this purpose.

5.1 Data collection and management

Source documents, where data are first recorded, include, but are not limited to, Ambulance Service Computer Aided Despatch (CAD) data, Ambulance service Patient Clinical Records (which may be

electronic or paper), hospital records and electronic correspondence. Source data shall be transcribed onto the Case Report Form (CRF) on the study database. The CRFs will be developed by the Chief investigators and the study statistician to collect all required study data.

Data from the ambulance service will be anonymised prior to being entered onto the study database.

The SCAS researcher will be made aware that a patient has been treated for cardiac arrest via one of the two mechanisms as outlined in section 3.1.1. It is anticipated that this should happen within 48 hours of treatment (or 3 days if the cardiac arrest happened over a weekend). Screening log completion will act as a safeguard to ensure that no cases are missed. This should happen within 7 days of cardiac arrest.

Once a case is identified, the SCAS researcher will access the patient's ambulance service clinical record and link this to the CAD data (via the incident number). From these sources, research paramedics will assess whether the patient meets study eligibility criteria and, if so, will transcribe cardiac arrest data, survival status and patient identifiers if the patient is not known to have died. Data from defibrillators will be accessed by the researcher. Quality of CPR measures will be transcribed from this source to the CRF by the researcher. The electrocardiogram (ECG) will be interpreted by the SCAS researcher and checked by a senior clinician. Confirmation of periods of ROSC will be sought from the patient clinical record. Prior to commencement of the study, the SCAS researcher and the senior clinician will review a number of example ECGs to ensure a standardised approach to assessment. Disagreement will be resolved through discussion or referral to a second senior clinician.

Information requests for patients not known to have died will be sent to the appropriate research team at the destination hospital. Information sought will include patient identifiers that the ambulance staff may have been unable to obtain, including survival status, patient location and date of transfer to the hospital ward. This will be sought by completion of a spreadsheet and will be sent securely via nhs.net email system. Ongoing checks regarding patient location and survival status will be made in order that a visit may be arranged at the appropriate time. Personal identifiers will only be shared between those in the direct care team, i.e. the ambulance service and the destination hospital, and not with the WCTU.

The mRS scores of surviving patients will be assessed at 30-days post event by the research paramedics using the Rankin Focussed Assessment (RFA) tool. This tool has excellent inter-observer reliability (unweighted κ of 0.93 (95% CI, 0.85-1.00)).[47] At 30 days, patients may have been

discharged home or they may be on the hospital ward. We will arrange to visit patients in either location to assess mRS. If the patient has been discharged home, two survival checks will first be made before telephoning the patient. Assessing mRS when they have been discharged into their home setting allows patients to accurately assess their abilities regarding their normal activities.[28] However, since the RFA encourages the gathering of information from all available sources it may also be reliably applied in the hospital setting.[47] Should the patient lack capacity at 30 days and remain in hospital the RFA will be completed with the consultee, nursing staff and the medical notes. Should they be at home, the opinion of the patient's consultee will be sought to complete the RFA. Where a proxy is required for mRS assessment, family members have been found to be more reliable than nurses or therapists.[48] A lone working risk assessment shall be carried out in accordance with the Warwick SOP. Home visits shall be carried out within office hours and within daylight hours where possible. Research paramedics shall ensure that they inform a member of the study team prior to entering an address, carry a mobile phone and undertake a dynamic risk assessment during the visit and inform the study team on leaving the address.

All documents will be stored safely in confidential conditions. On all study-specific documents, other than the signed consent, the participant will be referred to by the study participant number/code, not by name. mRS scores will be entered onto the study database and hard copy RFA sheets retained securely at site.

5.2 Database

The database will be developed by the Programming Team at WCTU and all specifications (i.e. database variables, validation checks, screens) will be agreed between the programmer and appropriate study staff.

5.3 Data storage

All essential documentation and study records will be stored by WCTU in conformance with the applicable regulatory requirements and access to stored information will be restricted to authorised personnel.

5.4 Data access and quality assurance

There is no requirement to collect personal information about potential participants. The only details required are call details and an assessment against the eligibility criteria. Information about enrolled participants will be collected by the research paramedics at site. Personal identifiable details will not be required for those patients known to have died. The purpose of gathering personal identifiable data regarding those patients not known to have died is to allow tracking

through hospital and follow up. Data will be gathered from source documents and entered directly onto the study database.

Information regarding patients not known to have died shall be shared between the site study team and the relevant research team in the destination hospital. The minimum data necessary to identify the correct patient and allow follow up shall be shared. This includes full name, date of birth, address, NHS number and GP surgery. Data will be shared between site and the destination on a password-protected spreadsheet via the secure nhs.net system. At the meeting to potentially grant consent, the research paramedic will seek a contact phone number and/or email address for the patient to allow follow up. This will not be necessary if this meeting coincides with the 30-day time point and the patient is still in hospital. Should contact with the patient's GP be required, to acquire outcome data if the patient has left hospital prior to being approached by a research paramedic and has not responded to invitation letters, identifiable information shall be shared with the GP to ensure correct patient identification.

Consent forms shall be securely stored at site with access only available to the site study team. They shall be securely shredded at study closure. Electronic documents shall be stored on the site server in a folder with access restricted to the study team only. Access permissions are granted/revoked by the Trust's IT team to remain secure.

Direct access to source data/documents may be required for study-related monitoring or audit by WCTU.

An electronic copy of the final study data set shall be sent to the participating ambulance service on completion of the study.

5.5 Data Shared with Third Parties

Anonymous, individual participant data that underlie the results reported in this article (text, tables, figures and appendices) will be made available to investigators whose proposed use of the data has been approved by an independent review committee identified for this purpose. Study data will be made available for five years following article publication. Proposals for data access should be directed to [contact]. Requestors will need to sign a data sharing agreement.

5.6 Archiving

After the study, site records shall be securely archived in accordance with GCP and retained for ten years. Electronic records shall be stored securely for ten years at site and at WCTU.

6. STATISTICAL ANALYSIS

6.1 Power and sample size

This feasibility study aims to recruit 90 patients, ideally 30 in each arm. This is in keeping with a recommendation of sample sizes of at least 50 for feasibility studies [27] whilst allowing a roughly equal number of patients to be recruiting into each arm. This should be both sufficient to ascertain whether recruitment is feasibly and achievable within a reasonable time scale.

6.2 Statistical analysis of efficacy and harms

6.2.1 Statistics and data analysis

There will not be a formal statistical analysis as the study has not been powered to assess difference in interventions. The analyses will be based on summary statistics, namely mean, standard deviation, median, interquartile ranges and missingness in the data. Where possible 95% confidence intervals will also be given.

6.2.2 Planned recruitment rate

The study aims to recruit 90 patients within a maximum two-year data collection period.

6.2.3 Statistical analysis plan

As this is a feasibility study there will be no interim analyses. However, a statistical analysis plan will be drawn out to illustrate how the data will be assessed, summarised and displayed.

6.2.3.1 Summary of baseline data and flow of patients

Baseline comparability of the randomised groups will be assessed using the following variables:

- Age (median and range)
- Sex (% male)
- Location of arrest (% private residence/ public place/ other)
- Witnessed vs. unwitnessed event (% witnessed and % bystander/ EMS or other healthcare provider/ unwitnessed)
- Bystander CPR vs. no bystander CPR (of those not EMS-witnessed, % provided BCPR prior to EMS arrival)
- Type of initial rhythm (% in VF/pVT, PEA or asystole)
- Time from call to application of defibrillator (median and range)
- Aetiology of cardiac arrest (% cardiac vs. non-cardiac cause)

Flow of patients will be presented using a consort flow diagram (<http://www.consort-statement.org/>).

6.2.3.2 Primary outcome analysis

The primary objective of this study is to establish whether it is feasible to conduct a large-scale definitive study. We will report the proportion of eligible patients who receive the randomised intervention.

6.2.3.3 Secondary outcome analysis

The secondary outcomes that will be assessed are:

- Treatment adherence rate. This will be assessed in terms of how many patients received the allocated first shock energy and, where more than one shock was delivered, how many received the correct subsequent shock energies.
- Data completeness of clinical outcomes below:
 - Neurologically intact survival at 30 days and hospital discharge (mRS score)
 - Return Of Organised Rhythm (ROOR) 2 min post shock

- Resulting rhythm (VF/pVT/PEA/asystole) 2 min post shock
- Re-arrest rate (re-fibrillation)
- Survived event (return of spontaneous circulation (ROSC) at hospital handover)
- Survived to hospital discharge and 30 days

These will be reported in terms of the proportion of patients for whom each of these outcomes was collected.

- Data completeness of process outcomes below:
 - Quality of CPR (chest compression rate, chest compression depth, chest compression fraction, pre-shock pause, post-shock pause)
 - Number of shocks
 - Advanced airway applied (% advanced airway applied and % supraglottic airway or endotracheal tube)
 - Intravenous medicines administered (% cases where medicines administered and % adrenaline, amiodarone)
 - Transported to hospital (% transported)
- Issues identified by ambulance staff and suggestions for study optimisation. These will be reported in terms of the topics identified, with example anonymised quotes, from the thematic analysis of the focus group data.
- Acceptability of approach to informing relatives of non-survivors. We will monitor the number and nature of enquiries received by the Ambulance Service, the time taken to identify next of kin, the sources consulted to verify next of kin details and the concordance/discordance between different sources.

6.3 Interim analysis and criteria for the premature termination of the study

No interim analyses are planned as this is a feasibility study. The study may be terminated prematurely for any of the following reasons:

- Mandated by the Ethics Committee
- The Study Oversight Committee decides that recruitment should cease
- Mandated by the sponsor

- Study funding ceases.

6.4 Subject population

This feasibility study aims to describe the study population in terms of:

- All-treated population: Any subject randomised and eligible for the study that received at least one part of the intervention
- Protocol-compliant population: Any subject who was eligible, randomised and received the protocol required intervention

The treatment of ineligible patients is outlined in section 2.4, above.

6.5 Procedure(s) to account for missing or spurious data

One of the aims of this study is to assess how much data might be missing following all reasonable attempts to collect this data. In order to prevent missing data, the following strategies will be employed:

- Monthly audits of routine ambulance service data will be conducted to ensure that there are no missing eligible cases. A site audit clerk will conduct these checks and report anonymised cases.
- A spreadsheet of data queries will be sent to the ambulance service on a monthly basis
- To maximise follow-up email alerts will be sent to the ambulance service reminding them that a patient has reached their 30-day assessment point

Where data cannot be obtained, reasons shall be recorded on the data queries sheet.

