2.2.2 Secondary objective

Secondary objectives of the study are to:

- To measure the rate of adherence to the allocated treatment
- Identify the best outcome measures in terms of ease and reliability of recording by reviewing data completeness.
- Explore what affects treatment adherence and data completeness by eliciting the views and experiences of paramedics via focus groups.

Figure 1 Study flow diagram

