3.4.1 Aims and objectives

Aim:

To explore and describe the experience of paramedics delivering this study, specifically the barriers and facilitators to patient recruitment.

Objectives:

- To explore strategies for optimising treatment adherence
- To describe problems and possible solutions for improving the ease and reliability of data recording.

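### A single completeness figure, taken after all retrieval efforts, shows whether an outcome can be obtained in the end and is a weak guide to how easy it is to record

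*Protocol*

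**What the plan says.** The second of the secondary objectives in protocol section 2.2.2 reads: "Identify the best outcome measures in terms of ease and reliability of recording by reviewing data completeness". Completeness is the only means that this objective names.

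Section 6.5 describes the quantity of interest: "One of the aims of this study is to assess how much data might be missing following all reasonable attempts to collect this data". Its retrieval step is "A spreadsheet of data queries will be sent to the ambulance service on a monthly basis". It also provides a prompt for the planned assessment, "To maximise follow-up email alerts will be sent to the ambulance service reminding them that a patient has reached their 30-day assessment point", and a log of failures, "Where data cannot be obtained, reasons shall be recorded on the data queries sheet". Section 5 adds a back-up source: "Outcome data for those patients missed in hospital will be sought by the Ambulance Service from the patient's GP".

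Section 6.2.3.3 lists the clinical outcomes and gives the reporting rule: "These will be reported in terms of the proportion of patients for whom each of these outcomes was collected". It sets no time point and plans no count of queries, time to retrieval or source used for these outcomes.

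Two other parts bear on ease. The qualitative sub-study in section 3.4.1 has as an objective "To describe problems and possible solutions for improving the ease and reliability of data recording". The Study Summary names, as measures for the same objective, a capture rate for shock data in clinical records and a completion rate for the Rankin assessment.

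**The concern.** The objective asks about ease; the reported figure answers a different question, namely whether a value was obtained by the end. A value found at first transcription and a value found after several monthly queries, or only by going to the GP, each add one to the same numerator. The work that separates them is not reported.

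Choosing outcomes for a definitive trial is a stated purpose of this study. Its planners need to know what a service records without prompting and how much effort closes the gap. A final percentage from about 90 patients at one ambulance service combines the two. An outcome that needed heavy chasing could be carried forward at a cost that only becomes apparent across several services.

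**Working it through.** The protocol states no completeness or recovery figure, so there is nothing to reproduce. The check has two parts.

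**1. What one final proportion can and cannot show.** Retrieval routes differ by outcome:

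- Rhythm outcomes come from defibrillator downloads, which may be attached to the record or accessed remotely or directly (section 3.1.1, Table 1).
- The mRS may come from the patient, a consultee, nursing staff or notes (section 5.1), or from records or the GP (Table 1).
- Outcomes missed in hospital are sought from the GP (section 5).

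The final proportion does not reveal which route was needed. By contrast, for next-of-kin details sections 3.3 and 6.2.3.3 do plan to monitor time taken, sources consulted and agreement between sources. No such measure of effort is planned for the clinical outcomes.

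**2. How far the gap can shrink.** Inputs: n = 90 (section 6.1). Assumed, because the protocol is silent: completeness before queries of 95% for an easy outcome and 60% for a hard one, and a share r of missing values recovered.

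Final completeness = p0 + (1 − p0) × r

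With the same r for both outcomes, final gap = initial gap × (1 − r), where the initial gap is 95 − 60 = 35 points:

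| r | Easy | Hard | Gap (points) |
|---|---|---|---|
| 0% | 95.0% | 60.0% | 35.0 |
| 25% | 96.25% | 70.0% | 26.25 |
| 50% | 97.5% | 80.0% | 17.5 |
| 75% | 98.75% | 90.0% | 8.75 |
| 90% | 99.5% | 96.0% | 3.5 |
| 100% | 100% | 100% | 0 |

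The two outcomes look alike only when nearly everything missing is recovered. At 90% recovery the Wilson 95% intervals with n = 90 are 95.0 to 100% and 89.7 to 98.5%. These only indicate precision. Both outcomes are measured in the same patients, so overlap of the intervals is not a test of the difference.

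Equal recovery is itself an assumption. With separate shares, the final gap is 0.40 × (1 − r_hard) − 0.05 × (1 − r_easy). This is below 0.35 whenever r_hard exceeds r_easy / 8 (from 0.40 × r_hard > 0.05 × r_easy). In this example the gap therefore narrows unless almost none of the hard outcome's missing values are recovered. In the extreme case of r_hard = 0 and r_easy = 1 it widens to 40 points.

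If half of the hard outcome's missing values can never be retrieved and the rest are, it finishes at 60% + 40% × 0.5 = 80% (Wilson 95% interval 70.6 to 87.0%) and still stands out.

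**The case against.** The strongest reply is that obtainability after reasonable effort is a legitimate target. A main trial would chase data too, so the final figure matters for choosing outcomes. That stands, and the final figure should be kept.

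A reader might infer that completeness is assessed only after chasing, that hard outcomes will end up looking as complete as easy ones, and that the objective therefore cannot be met. The protocol does not support this:

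- Section 6.5 calls final missingness one aim among others, and section 6.2.3.3 fixes no time point.
- Near-equality needs almost total recovery. A query cannot create a rhythm strip or a handover status that was never recorded, and consent to follow-up may be refused.
- The monthly audits in section 6.5 look for missed eligible cases, not missing values, and the email alerts prompt a planned assessment. Of the steps listed there, only the query sheet recovers values.
- The objective is to identify the best measures, not to rank them formally.
- The focus groups, the logged reasons and the Study Summary's shock-data capture rate all bear on ease.

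These other sources help only in part. The focus groups give ambulance staff's views, whereas a researcher reads the ECGs and research paramedics assess the mRS. Reasons are logged only for failures, so the effort behind recovered values goes unreported. The Study Summary's capture rate covers shock data alone and is not carried into section 6.2.3.3 in those terms.

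It can also be said that this belongs in the statistical analysis plan or the Data Management Plan, both of which the protocol promises. That is right for table layout. But the protocol itself fixes the metric, and first-pass status has to be captured while data are being collected. The protocol does not say that it is kept.

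**Conclusion.** The point holds as a weakness of measurement. As written, sections 6.5 and 6.2.3.3 lead to one proportion per outcome that reflects eventual obtainability. It understates differences in ease where queries or back-up sources recover missing values.

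The size cannot be fixed from the protocol. Under the assumed starting values and equal recovery, a 35-point difference in first capture appears as anything from 26.25 points (25% recovery) to 3.5 points (90% recovery). Where values were never recorded, the difference remains visible. The objective is poorly served rather than out of reach, and the change below is worth making because the outcomes of a larger trial would be chosen on this evidence.

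**What to change.** In sections 6.2.3.3 and 6.5, report completeness for each outcome at two points:

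- **(a) First scheduled collection, before any query on that item.** For prehospital and defibrillator outcomes, this is first transcription from the source record. For survival and mRS at discharge and 30 days, it is the first scheduled assessment, among patients who have reached it and for whom follow-up is permitted. One cut-off at first extraction for every outcome would count 30-day data as missing before they were due.
- **(b) Database lock.**

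Date-stamp entries so that (a) can be recovered. For each outcome, give the number of queries raised or the back-up source used, and tabulate the reasons already logged on the query sheet. State that both figures will be used when choosing main-trial outcomes.

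The cost is date-stamping during collection and a few extra table columns, built on query sheets that are already planned. The first-pass figures will look less favourable than the final ones. For prehospital items they will also partly reflect delays in transcription and linkage, which should be said when they are reported.
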